#### **9.5 Missing Data**

Prior to performing any outcome analyses, we will evaluate the amount, reasons, and patterns of missing data. Missing data unrelated to the outcome of interest will be considered missing completely at random, and complete case analysis will still generate unbiased estimates. We will conduct sensitivity analyses to compare estimates of treatment effects with and without multiple imputation to assess the effect of missing data on statistical inference.

We propose a GLMM to analyze data, the main advantages being unbiased estimates when there are missing outcomes during the follow-up period if the probability of missing is not related to the outcome value. For the missing values at the baseline or partial baseline collected data, we will use a multiple imputation approach. Models will also be run on the raw, non-imputed data with full information maximum likelihood estimation. Inferences for the trial arm, wave, and interaction between trial arm and wave do not differ between the analyses of the raw and multiply imputed data. Rates of reduction will be calculated from population-averaged rates, which control for all other covariates in the multivariable model. Models will be calculated by using the GLIMMIX and MIANALYZE procedures in SAS, version 9.4, and model fit will be evaluated by diagnostic statistics and residual plots.

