### **3.0 STUDY DESIGN**

#### **3.1 Randomized Control Trial**

We will conduct a small-scale digital RCT to evaluate the feasibility of the mLab App Plus and testing/linkage to care uptake as compared to the control arm (receiving SOC). We will enroll 40 YMSM and YTGW (ages 18-39) who report being negative for HIV and syphilis, or whose statuses are unknown, and randomize them into the intervention or control condition. The trial includes screening, a baseline appointment, and a 3-month follow-up appointment.

**Intervention Condition:** Participants randomized to intervention will be provided with the mLab App Plus, and a box of condoms. The intervention arm will also complete two HIV/Syphilis Ab Combo Rapid Tests (DPP® HIV-Syphilis Test) at their baseline (1st test) and 3-month follow-up (2nd test) appointments in the clinic (more details in section 5.4 Intervention/Investigation Procedures).

**Control Condition:** Participants randomized to standard care will be sent an email with links to mobile-optimized online prevention information, including PrEP and HIV/STI testing information found on the CDC website, and a box of condoms .

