#### **3.2 Study Randomization**

After providing informed consent, participants will be randomized to study arms in a 1:1 ratio of intervention to control arms. To reduce opportunities for selection bias, we will use a variable permuted randomization block design where block size itself is randomly selected (i.e., blocks of four to eight). The advantage of a permuted block design is that treatment assignment is pre-determined before the trial begins and assignment remains static throughout the trial. Both groups will receive standard care HIV/STI testing-related risk reduction counseling, a box of condoms, and PrEP assessment. The intervention group will self-administer their first DPP® HIV-Syphilis Test under the supervision of a trained clinician at baseline and again at their 3-month follow-up. No control group participant will be offered HIV or Syphilis testing in order to observe intervention outcome.

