### 3-Month Follow Up Visit

The *3-Month Follow Up* survey will include questions on demographics, health literacy sexual risk behaviors including number of men (and other genders) they engaged in anal or oral sex with, and condomless anal intercourse, as well as questions on PEP/PrEP use and adherence, drug and alcohol use, and HIV Risk Index. Participants randomized to both the control arm and intervention arm of the study will all participate in the questionnaire at the 3-month time point. The survey will also inquire about participants' opinions towards HIV/STI testing since the baseline visit and their experiences using the mLab App Plus, if they are randomized to the intervention arm.

Following completion of the survey, intervention arm participants will once again self-administer the DPP® HIV-Syphilis test at the clinic in the presence of a clinician. They will follow the same testing procedure as they did at baseline and a study team member will meet with them to discuss results and set up confirmatory testing, if necessary, once they have completed their DPP® HIV-Syphilis test. Results are stored on their smartphone through the mLab App Plus and securely transmitted and stored on the REDCap Server.

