# YMSM/YTGW attending other HIV/STI prevention service appointments
# YMSM/YTGW accessing HIV/STI prevention or social service appointments (e.g., PEP, PrEP, STI testing, mental health counseling, drug treatment, job assistance, education services, job skills training, housing assistance)
Outcome indicator data disaggregated by race/ethnicity, age, testing history and geographical area
Additional HIV-associated health outcomes (e.g., sexual behaviors associated with HIV transmission)

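### For secondary outcomes surveyed at both visits, the arm-by-wave terms named in section 9.5 give a less precise between-arm effect than adjusting the 3-month value for baseline

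*Combined protocol and SAP*

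**What the plan says.** Section 9.5 (Missing Data) introduces the model with "We propose a GLMM to analyze data". It names terms only once, in a sentence about "Inferences for the trial arm, wave, and interaction between trial arm and wave". That sentence goes on to say that these inferences agree between the raw and the multiply imputed data. The section then refers to population-averaged rates, "which control for all other covariates in the multivariable model", but lists no covariates. It does not say that the arms share a baseline mean or that the baseline value of an outcome is a covariate.

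On timing, section 3.1 states: "The trial includes screening, a baseline appointment, and a 3-month follow-up appointment". Table 1 in section 5.4 shows the survey at both visits in both arms. The baseline and 3-month surveys share questions on sexual risk behaviours and the HIV Risk Index, "as well as questions on PEP/PrEP use and adherence, drug and alcohol use". Table 2 (section 6.2) includes "Additional HIV-associated health outcomes (e.g., sexual behaviors associated with HIV transmission") among the outcomes.

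Section 9.4 gives the testing comparison to logistic regression, with no wave term. No other between-arm analysis is specified for the survey outcomes measured twice.

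**The concern.** With a single follow-up, a wave effect can be estimated only if baseline is itself a wave, so the baseline value belongs to the outcome vector. If an arm main effect is also fitted, each arm has its own baseline mean, and the interaction equals the between-arm difference in mean change.

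That contrast subtracts the whole of any chance baseline difference, although only a fraction r of it is expected to persist to 3 months. With about 20 per arm, chance differences can be sizeable. Adjusting for other covariates does not cure this, because the baseline value of the outcome is not among them.

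At stake is the width of the intervals for the secondary behavioural outcomes in a trial of 40 people. A baseline-adjusted analysis would get more from data that are already collected.

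**Working it through.** **Inputs from the documents**
- Sample size: "We will enroll 40 YMSM and YTGW (ages 18-39"), section 3.1.
- Allocation: "participants will be randomized to study arms in a 1:1 ratio of intervention to control arms", section 3.2. This gives n = 20 per arm.
- Two waves: baseline and 3 months (section 3.1, Table 1).
- The plan states no standard error, power or effect size for these outcomes, so there is no figure of its own to reproduce.

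**Assumptions**
- r is not in the documents; 0.3 to 0.9 is used.
- The linear case assumes equal variance at both visits and in both arms, and no dropout.

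**Formulas, in SD units**
- Difference in change (unconstrained interaction): SE = √[(2/n)·2(1−r)].
- Baseline-adjusted: SE = √[(2/n)(1−r²)].
- Variance ratio: 2(1−r)/(1−r²) = 2/(1+r).
- 95% half-width = 1.96 × SE.

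**Results at n = 20 per arm**

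| r | SE, change | SE, adjusted | Half-widths | Variance ratio | Simulated SE ratio |
|---|---|---|---|---|---|
| 0.3 | √0.140 = 0.374 | √0.091 = 0.302 | 0.73 vs 0.59 | 1.54 | 1.23 |
| 0.5 | √0.100 = 0.316 | √0.075 = 0.274 | 0.62 vs 0.54 | 1.33 | 1.15 |
| 0.7 | √0.060 = 0.245 | √0.051 = 0.226 | 0.48 vs 0.44 | 1.18 | 1.08 |
| 0.9 | √0.020 = 0.141 | √0.019 = 0.138 | 0.28 vs 0.27 | 1.05 | 1.01 |

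The last column comes from 4,000 simulated trials with the baseline slope estimated, so it includes the cost of that extra parameter. Comparing 3-month values alone has SE √(2/20) = 0.316. The change contrast is less precise than that whenever 2(1−r) > 1, that is, when r < 0.5.

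With an assumed 15% dropout (17 per arm), both SEs rise and the formula ratio is unchanged: 0.343 vs 0.297 at r = 0.5.

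**Binary outcomes.** Assume prevalence of 60% at baseline and 50% at 3 months, and work on the risk-difference scale. The change contrast has variance (2/20)[0.24 + 0.25 − 2r√(0.24·0.25)]; the adjusted one has (2/20)·0.25(1−r²). Half-widths are 36.3 vs 29.6, 30.7 vs 26.8 and 23.8 vs 22.1 percentage points at r = 0.3, 0.5 and 0.7. Simulation gave 36.6 vs 30.2, 31.1 vs 27.3 and 23.7 vs 22.5. On the logit scale, a large-sample simulation gave efficiency ratios of 1.65, 1.42 and 1.32 at observed correlations of 0.17, 0.38 and 0.53. That is a proxy for the planned model, not a GLIMMIX fit.

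**Where nothing is lost.** Eligibility (section 4.1) requires no HIV or syphilis test in the past 3 months. Recent testing is therefore the same for everyone at baseline, and on the risk-difference scale the interaction equals the 3-month difference.

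**The case against.** The sentence in section 9.5 is about robustness to imputation. It does not call the interaction the test of the intervention, and it does not say which outcomes the GLMM serves. The unlisted covariates could in principle include a baseline value, and unconstrained baseline means are implied rather than stated. This stands. It makes the point conditional on the natural reading of the named terms, and it is itself a reason to state the contrast.

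A reader might infer that every surveyed outcome is affected, or that the loss falls on the trial's main effect size. The documents support neither:
- App experience is asked only at 3 months and only in the intervention arm.
- The linkage and service outcomes in Table 2 have no stated baseline measure.
- The primary outcome requires the DPP test, which controls do not receive.
- Aim 2 (section 1.3) seeks effect sizes for testing uptake, which section 9.4 analyses by logistic regression. The effect-size goal in section 9.2 therefore cannot simply be carried over to the behavioural outcomes.

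A reader might also infer that baseline adjustment is better in every respect. Section 5.1 places the baseline survey after randomisation, and the documents do not say whether participants know their arm when they answer. If that knowledge shifted answers by d at both visits, the change contrast would cancel it, while the adjusted estimate would keep (1−r)d. If only the baseline answers shifted, the change contrast would be off by d and the adjusted estimate by r·d. The two are exposed differently, and neither is safer in all cases.

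Finally, the planned model may be logistic. Adjusting for baseline then changes what the odds ratio estimates, and baseline adjustment and the common-baseline model are no longer interchangeable. This also stands, and the fix allows for it.

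**Conclusion.** The point holds for secondary outcomes surveyed at both visits, and only for those. Read as an unconstrained two-wave model, the terms in section 9.5 yield a difference in change. Its standard error at 20 per arm is about 23%, 15%, 8% and 1% larger than with baseline adjustment for r = 0.3, 0.5, 0.7 and 0.9. The loss is material at low to moderate correlation and negligible near 0.9.

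The sizes rest on an assumed r, a linear model with equal variances, and baseline answers not influenced by arm. The direction is the same in the binary checks. The primary outcome and the testing comparison are untouched.

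**What to change.** In section 9.5:
- Name the outcomes that the GLMM serves.
- For those surveyed at both visits, define the between-arm effect as the 3-month value adjusted for the participant's own baseline value. Alternatively, keep the longitudinal model with a common baseline mean (wave and arm-by-wave, no arm main effect). Choose one in advance.
- Report the effect with a 95% CI. For binary outcomes, give a standardised risk difference so that adjustment does not alter the estimand.
- State the assumption that baseline answers are not influenced by arm, since the survey follows randomisation, and keep the arm-by-wave change contrast as a sensitivity analysis.

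The cost is a few sentences, one model degree of freedom for the baseline value, and reliance on that assumption. No new data or participants are needed.

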## **10.0 Human Subjects Protections**

### **10.1 Informed Consent**

The informed consent of each participant will be obtained in accordance with 21 CFR Part 50 and the Declaration of Helsinki before protocol-specified procedures are carried out. An investigator will obtain the participant's written informed consent prior to any study-related procedures. Consent will be documented by the dated signature of the subject. The signature confirms that the consent is based on information that has been understood. Each participant's signed informed consent form will be kept on file by the investigators for possible inspection by regulatory authorities.

The study plan, advertisements, or recruitment letters, lay description of the study, and all consent forms will be submitted to the IRB following proposal acceptance and prior to study initiation. [name] will be responsible for obtaining IRB approval for this study. Recruitment for study participation will occur following IRB approval. The investigators will determine eligibility for inclusion, explain the purpose of the study, answer any questions, and obtain e-consent from the participants. Patients who agree to participate will sign a consent form. Potential risks and strategies for risk management will be carefully explained as part of informed consent procedures. All HIPAA requirements will be applied to this study.

We will assure potential participants in these study activities that their willingness to participate and/or to complete the study activities will not have an impact on their participation in other aspects of the study or on their employment or student status at study sites.

### **10.2 Vulnerable Subjects: Protecting Against/Minimizing Potential Risk**

Ethnic and racial minority populations will be enrolled. While this group is considered a vulnerable population, the study team has considerable experience enrolling these participants. The study will be conducted according to Good Clinical Practice guidelines, the U.S. Code of Federal Regulations (CFR) Title 21 CFR (Part 50 – Protection of Human Subjects and Part 56 – Institutional Review Boards) and the Declaration of Helsinki.

### **10.3 Risks**

#### **10.3.1 General risks**

There may be risks or discomforts in participating in this study. Participants may feel uncomfortable with completing some questions in the survey. Participants may skip any HIV/STI information or

questions that may make them feel uncomfortable or stop the research procedure. People around may observe participants using the mLab App Plus. If participants are concerned about people seeing them use of mLab App Plus, it is important that they access the application in private location.

#### **10.3.2 Loss of confidentiality**

A risk of taking part in this study is the possibility of a loss of confidentiality or privacy. Loss of confidentiality or privacy means having personal information shared with someone who is not on the study team and was not supposed to see or know about your information.

#### **10.3.3 Venipuncture**

There is a small risk of local hematoma or infection associated with blood sampling. On rare occasions, drawing blood can cause dizziness, presyncope, and even syncope.

### **10.4 Benefits**

#### **10.4.1 Potential Benefits of the Proposed Research to Research Participants and Others**

The potential benefits to an individual participant in the study are not known. The potential benefits of the study to others could be considerable. If our hypotheses are true, this study will make a significant contribution towards preventing HIV and syphilis in YMSM.

This study has not been designed for the direct benefit of its participants; however, there are several ways in which they may derive benefit. The proposed research will increase knowledge of HIV and syphilis testing among YMSM. The knowledge gained will contribute to the body of knowledge regarding the use of health information technology for improving the lives of MSM at risk for HIV and syphilis. The avoidance of HIV and syphilis through study participation will be a significant personal benefit to participants.

#### **10.4.2 Importance of Knowledge to be Gained**

The knowledge gained from this research will enable the scientific community, clinicians, and high- risk populations to prevent new HIV and syphilis infections in the US.

### **10.5 Participant Privacy and Confidentiality**

#### **10.5.1 Access to individually identified private information about human subjects**

Access to individually identified private information about human subjects will be limited to research team members who collect and manage the data, study staff, site principal investigators and the Principal Investigator. Coded data will be accessible to all members of the research team involved in the data analysis. Our study team is extremely prudent in keeping participant data secure and confidential. All laboratory specimens, evaluation forms, reports, and other records will be identified by a unique coded number to maintain participant confidentiality. The material, records, and data obtained through participation in the study will be specifically for research purposes. Existing health records may be used with the permission of the participants. Materials will be obtained by trained clinical staff at each study site. Data will

be stored using Research Electronic Data Capture (REDCap) at each respective performance site, and then the completely deidentified data will be merged at CUIMC. All laboratory specimens will be identified only by the identification number. The code linking the participant identification number to participant identifying information (name, address, etc.) is maintained at the clinical sites through REDCap, and only authorized site personnel have access to the code. Limited individually identifiable private information is collected that is essential for processing participant payments and for analysis purposes.

#### **10.5.2      Confidentiality of the App**

The App requires a password. All study data will be encrypted and stored on secure HIPAA- compliant servers at the CUIMC campus. All study data will be kept in password-protected computers or file cabinets in locked offices and will be maintained in a completely secure and HIPAA-compliant environment. All CUIMC servers have HIPAA-compliant security. Nonetheless, there is always the risk of a data breach, so we will make our study participants aware of this risk upon enrollment.

#### **10.5.3      Confidentiality and privacy of the study data**

All study data will be stored in password-protected computers or file cabinets in locked offices. Audio recordings of interviews or focus groups will be destroyed once data are transcribed and analyzed. All research team members will pass the protection of human subjects and HIPAA research exams and sign a protocol-specific conflict of interest. Risks will be minimized by not including personal identifying information on the forms, when possible, and by conducting interviews and collection of personal information in a private setting. All data will be collected using unique patient identification codes. All laboratory specimens, evaluation forms, reports, and other records will be identified by a coded number to maintain participant confidentiality. All records will be stored in a locked file cabinet. Study data from both sites will be collected and managed using REDCap. REDCap is a secure web application designed to support data capture for research studies, providing user-friendly web- based case report forms, real-time data entry validation (e.g., for data types and range checks), audit trails, and a deidentified data export mechanism to common statistical packages (SPSS, SAS, Stata, R/S-Plus). REDCap data collection projects rely on a thorough study- specific data dictionary defined in an iterative self-documenting process by all members of the research team. This iterative development and testing process results in a well- planned data collection strategy for individual studies. REDCap also includes a powerful tool for building and managing online surveys. The research team can create and design surveys in a web browser and engage potential respondents using a variety of notification methods. REDCap is flexible enough to be used for a variety of types of research and provides an intuitive user interface for database and survey design and data entry. Lastly, clinical information will not be released without written permission of the participant, except as necessary for monitoring by the IRB or the CDC.

#### **10.5.4      Plan for privacy and data security**

Beginning with the development process and throughout the research project, we will follow the privacy and security principles set forth at healthhit.gov. Our team is familiar with the importance of the privacy and security of personal health information to engender individual trust in the use of health IT applications. We have expertise and experience in this domain as we have developed several health IT systems funded through NIH and the Agency for Healthcare Research and Quality for persons living with HIV whose personal health information is usually held to higher security standards than traditional patients as HIV has historically been a stigmatized disease. We built the the mLab App Plus (NIMH

R01MH118151) which is housed on the CUIMC IT servers. Study data from mLab App Plus will be stored on the CUIMC servers. The CUIMC servers are in a secure datacenter, with necessary redundancies. Currently the network can be accessed remotely via Virtual Private Network with a Citrix solution being developed. All servers have HIPAA compliant security.

CUIMC has an Information Security Office (ISO) that facilitates all aspects of information security risk management at CUIMC, with a particular focus on threat management and HIPAA compliance. This includes administration and enforcement of information security policies on campus.

The Information Security Office also provides guidance to CUIMC schools and departments regarding any information security concerns they may have. The ISO collaborates with the entire CUIMC community to protect the confidentiality, integrity, and availability of critical information and computer resources. The ISO strives to implement secure computing infrastructure and practices with sensitivity to CUIMC's educational and research environment. Columbia University has an information security charter which is the foundation of all the work carried out by [name] and her research team. In specific, [name] will work with the CUIMC IT server group and the information security office to protect the confidentiality, integrity, and availability of participants' data. Confidentiality means that information is only accessible to authorized users. Integrity means safeguarding the accuracy and completeness of data and processing methods. Availability means ensuring that authorized users, such as research participants, have access to data and associated information resources when required.

Prior to consent, study participants will be informed as to what data the App will collect. Data will be encrypted and stored securely on the CUIMC IT servers. As a starting point for ensuring privacy and security, all smartphones will be password-protected. In addition, there will be an additional password for the App so that only study participants will be able to open the App.

